Title: Comparative effects of integrated physical training with high protein diet versus low protein diet in COVID-19 asymptomatic older adults with Sarcopenia symptoms.

Clinical trial registration number: NCT05224453

Date: 12/02/2022

Study Protocol

Background: Sarcopenia is the major health concern and common consequence of COVID-19 in the aging population. Moreover, this clinical condition has not been considered in usual physical rehabilitation practice and nor its optimal protein requirement in food is well defined, which requires a meaningful study in this field.

Objective: To find and compare the clinical and psychological effects of integrated physical training with a high protein diet versus low-protein diet in community dwelling COVID-19 asymptomatic older adults with Sarcopenia symptoms.

Design: It is a single-blinded, randomized, experimental study performed during March -2020 to November-2021. The trial received acceptance from the department of ethical committee (DEC), Prince Sattam bin Abdulaziz University, Al-Kharj, Saudi Arabia with an approval number of RHPT/020/51. The DEC approved the subject consent form, treatment protocols and the outcome parameters measured in the trial. The trial was executed in accordance with the ethical guidelines laid down in the 1964 Declaration of Helsinki and was registered in the clinical trial registry with registration number NCT05224453. The finally selected subjects for the trial were asked to fill the written subject consent form and underwent measurements for pre interventional personal and anthropometric data. A two block simple random sampling method was used to randomize and allocated the participants into two treatment groups. The group A was treated with integrated physical training with high protein diet (n = 38) and the group B was treated the same integrated physical training with low protein diet (n = 38) for a duration of eight weeks.

Subjects

Subjects for the study were received from local and government hospitals in Al-Kharj and Riyadh region of Saudi Arabia. Positively diagnosis of asymptomatic COVID-19 male patients

with 60 – 80 years of age was recruited for the study. Appendicular skeletal muscle mass index (ASMI < 7.0 kg/m²) was used to identify sarcopenia (skeletal muscle loss). Sarcopenia was diagnosed according to the guidelines given by the Asian working group for Sarcopenia (AWGS). Patients with less muscle mass, low hand grip strength (< 24 kg) and decrease walking speed (< 0.7 m/sec) were involved. Subjects with a history of physical workout, taking medicines, recent surgeries and joint problems in leg, heart and lung problems, neurological issues, any other systemic diseases and contraindications for physical training were eliminated from the study. The fig-1 depicts the methods and procedure of involving study subjects in this trial.

Intervention

Subjects in group-A and Group-B (n=38) underwent integrated physical training for 8 weeks. A trained physiotherapist executed the training protocols under proper COVID instructions. The training protocol was recorded in treatment logbook and was assessed each session by the study supervisor. Prior to the start of exercise training, the basic tests such as; body temperature, blood-pressure, oxygen saturation rate, heart beat and physical fitness were recorded. If these scores exceeded the normal values such as, like body temperature > 38.0°C, blood-pressure > 150/100mmHg and heart beat >90 beat per min or < 50 beat per min, subjects were asked to refrain from training on that session.

The maximum heart rate (MHR) was used to measure the intensity of the given exercise. It was found by reducing the subject's age from number 220. Aerobic training was given with 40 to 50 percent of maximum heart rate for all the subjects, which is considered as low-intensity aerobic training (LAT). Every day, the intervention started with 10mins of stretching of upper and lower limb muscles. Subsequent to stretching, the subjects were asked to do 30 mins of LAT; consisting of 20 mins of treadmill (Axos, Kettler Runner, China) and 10 mins of cycle ergometer (Axos, Kettler Runner, China), then with 10 mins of cool down.

All the participants, in both the groups, were prescribed with strength training exercises with resistance depends upon each subject's individual muscle assessment. The ideal resistance for each muscle groups were measured based on 1 repetition maximum (1RM) principle. The important muscle groups in the spine, upper and lower limb were trained. Each muscle group was undergone training for 3 sets consisting 10 repetitions in each set, with a relaxation of 5 mins rest between sets. The weight was gradually increased as per the subject and therapist needs and the exercise was performed for 4 days in a week for 8 weeks.

In addition to the integrated physical training exercises, group A received a high protein diet in the range of 1.1 – 1.3 g/kg protein/ ideal body weight/day (>1 g/kg aBW/d) and group B received low protein diet in the range of 0.7 – 0.9 g/kg protein/ ideal body weight/day (<1 g/kg aBW/d) as prescribed by a qualified nutritionist.

Outcome measures

Hand grip strength: The test is easy to perform and a less expensive one. It measures the strength of upper extremity by using a device handheld dynamometer. The participant was instructed to press the hand piece of the dynamometer to the maximum of his ability and the values shown on the display were recorded. Three values were noted for each participant and the mean value was considered for interpretation and it is a reliable and valid tool to measure the strength of upper extremity.

Muscle cross sectional area - CSA: Muscle CSA is measured with Magnetic resonance imaging (MRI) scan and it is an expensive measurement. The CSA of three major muscle such as; half way at arm - biceps, thigh - quadriceps and calf muscles were measured and included for analysis.²³

Kinesiophobia: TSK – 11; Tampa scale of kinesiophobia questionnaire was administered to find the level of fear of movement of participants. The questionnaire has eleven items, which measures the mindset at various activities in four point likert scale. Maximum score indicates high level of fear whereas the minimum score indicates low level of fear during activities.

Quality of life: Sarcopenia quality of life (SarQol) questionnaire was used to measure the subjects' wellbeing. The participants filled the questionnaire themselves and it is a robust tool to measure Qol.

Sample size

The sample size for the study was decided based on the report from the study by Yoo Jet al. Thirty-five subjects in each group were found by assuming forty percentage mean improvement in handgrip strength with standard deviation of 2. By accepting 10% drop of subjects at 6 month follow up, two subjects were added in each group. Hence, N=76 subjects were selected and divided into two groups with n=38. The sample size was calculated with the statistical power at 80% with α level of 0.05. The whole analysis was done with G*Power - version 3.1.9.7 software.

Statistical analysis plan

Subjects' personal and anthropometric measurements were calculated through Kolmogorov–Smirnov test for testing homogeneity and the data were represented in tabular form. The measurements were taken before intervention, during intervention at 4 weeks, after intervention at 8 weeks and after 6 months follow up. The data were shown as mean and standard deviation with 95% confidence interval (CI) with upper and lower limit. The time and group (4 × 2) multiple analysis of variance (MANOVA) of primary and secondary variables are reported between group A and group B at various intervals. Student's t test was used to calculate inter-group effects and repeated measures (rANOVA) was used to calculate the intra-group effects. IBMSPSS – online version 20 was used to do all the statistical tests and α level was set at 0.05.

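### The drop-out step does not add up: 35 plus 2 is 37 per group (74 in total), not the stated 38 (76)

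*Combined protocol and SAP*

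**What the plan says.** The Sample size section builds the trial's size in three steps.

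1. The calculated number: "Thirty-five subjects in each group were found by assuming forty percentage mean improvement in handgrip strength with standard deviation of 2", at 80% power and an α of 0.05, using G*Power.
2. The drop-out allowance: "By accepting 10% drop of subjects at 6 month follow up, two subjects were added in each group".
3. The result: "Hence, N=76 subjects were selected and divided into two groups with n=38".

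The final group size is repeated elsewhere. The Design paragraph gives 38 for the high-protein arm: "The group A was treated with integrated physical training with high protein diet (n = 38"). It gives the same number for the low-protein arm, and the Intervention section gives it again: "Subjects in group-A and Group-B (n=38) underwent integrated physical training for 8 weeks". The document offers no other addition or reason that would account for a further subject per group.

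**The concern.** The third step is presented as following from the first two, and it does not. The calculated number, the number added and the final number cannot all be right, so a reader cannot tell what the calculation returned or how much loss was allowed for.

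Nor can the reader settle it by recomputing the 35. The section gives a percentage improvement and a standard deviation, but no baseline mean, absolute difference, named test or sidedness. This paragraph is the only justification given for the trial's size, and its drop-out sentence refers specifically to the 6-month visit. Anyone judging the 6-month results would look to it to see what attrition was planned for.

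**Working it through.** **Inputs, all from the Sample size section:** calculated number 35 per group; 2 added per group; anticipated loss 10% at 6 months; final number 38 per group, 76 in total.

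**1. The plan's own sum**
- Per group: 35 + 2 = 37, against the stated 38.
- Total: 2 × 37 = 74, against the stated 76.

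The stated figure is not reproduced. These are whole numbers given in the text, so the sum should be exact.

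**2. Could rounding explain it?**
- Multiplying up: 35 × 1.10 = 38.5. Rounded up this is 39, which adds four. Cut to 38, it adds three.
- Dividing by the retained fraction: 35 / 0.9 = 38.9, so 39, which adds four.
- Reading the two as a total for both groups: 70 + 2 = 72, further from 76 and contrary to the text.

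No variant reaches 38 by adding two to 35.

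**3. Which sums do give 38?**
- 35 + 3 = 38 (the number added is wrong), or
- 36 + 2 = 38 (the calculated number is wrong).

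Nothing in the document mentions 36, but nothing rules it out. The repeated 38 supports the total and does not separate these two routes.

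**4. Conditional check: does 38 cover a 10% loss?** This matters only if the calculated number was meant to be evaluable at 6 months. The plan does not say at which visit it is powered.

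Expected number left: 38 × 0.9 = 34.2 per group.

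| If the calculated number is | Added to reach 38 | Loss covered | Needed for 10% loss | Expected shortfall per group |
|---|---|---|---|---|
| 35 | 3 | 3/38 = 7.9% | 35/0.9 = 38.9, so 39 | 35 − 34.2 = 0.8 |
| 36 | 2 | 2/38 = 5.3% | 36/0.9 = 40 | 36 − 34.2 = 1.8 |

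**5. Illustrative power at 34 per group.** Assume a two-sample t test at α = 0.05, and choose the standardised difference that gives exactly 80% power at the calculated number. Then evaluate power from the noncentral t distribution with 34 per group (2 × 34 − 2 = 66 degrees of freedom).
- Calculated number 35: 78.82% two-sided, 78.96% one-sided.
- Calculated number 36: 77.65% two-sided, 77.94% one-sided.

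The loss is therefore about 1 point at most in the first case and about 2 points at most in the second. It is smaller still if the calculated number is merely the smallest that reaches 80%. The plan states neither the test nor the effect size, so these figures show scale only.

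**The case against.** The strongest reply is that this hardly matters. The gap is one subject per group, the stated size is larger than the literal sum, 38 is used consistently, and nothing in the Statistical analysis plan depends on the number added. All of that is true. It limits the severity, but it does not make the sum correct.

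It can also be said that 36 appears nowhere, so that route is conjecture. That is fair: it is a possibility only. But the text does not rule it out, and this is why the output should be checked before either number is changed.

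A third reading is that 37 was the target and 38 were simply recruited, leaving 35 and two both correct. The text makes this unlikely, because it presents 76 as the consequence of the preceding figures. It cannot be excluded, though, and the same check of records would reveal it.

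Finally, whether 38 covers a 10% loss is a separate question from the addition, and the power figures rest on an assumed test. Both points stand, and both results are conditional. There is also merit in keeping 10% on record as the planning expectation. The corrected sentence should therefore still report what a 10% loss would leave.

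**Conclusion.** The derivation is wrong as written. The definite discrepancy is 37 against 38 per group, and 74 against 76 in total. It rests on no assumption beyond the plan's own figures. It does not show that 37 is the right target; the error more probably lies in the 35 or in the two.

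The adequacy of the allowance depends on the calculated number being required at 6 months. On that assumption, 38 per group covers about 8% loss (base 35) or about 5% (base 36) instead of 10%, an expected shortfall of 0.8 or 1.8 subjects per group.

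The severity is minor. The Design paragraph describes the trial as "performed during March -2020 to November-2021", the group size is consistent, and no analysis changes.

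**What to change.** Check the original G*Power output and correct whichever figure is wrong, so that the calculated number, the number added and 38 agree.

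- If the output shows 35: *Three subjects were added to the calculated 35 in each group, giving 38 per group (N=76); this allows for about 8% loss (3/38), and a 10% loss would leave about 34 per group at 6 months, slightly fewer than the calculated 35.*
- If the output shows 36: *Two subjects were added to the calculated 36 in each group, giving 38 per group (N=76); this allows for about 5% loss (2/38), and a 10% loss would leave about 34 per group at 6 months, fewer than the calculated 36.*
- If the records show that 37 was planned and 38 were enrolled, say so plainly.

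Give a power figure for the 6-month visit only if it is recomputed from the original G*Power inputs. Enrol no more subjects.

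The cost is one check and one corrected sentence, with no change to any analysis. With either of the first two wordings, the allowance is described as about 8% or about 5% instead of 10%.

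### The plan expects 10% loss by 6 months but has no missing-data rule; its MANOVA and rANOVA would by default drop men missing any visit, so its tests can rest on different sets of men

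*Combined protocol and SAP*

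**What the plan says.** All of the relevant text is in the Sample size and Statistical analysis plan sections.

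- Expected loss: "By accepting 10% drop of subjects at 6 month follow up, two subjects were added in each group". The final size follows: "Hence, N=76 subjects were selected and divided into two groups with n=38".
- Visits: "The measurements were taken before intervention, during intervention at 4 weeks, after intervention at 8 weeks and after 6 months follow up".
- Time-by-group analysis: "The time and group (4 × 2) multiple analysis of variance (MANOVA) of primary and secondary variables are reported between group A and group B", at the various visits.
- Remaining tests: "Student's t test was used to calculate inter-group effects and repeated measures (rANOVA) was used to calculate the intra-group effects".
- Software: all tests are run in SPSS version 20.

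The document names no analysis population, no intention-to-treat rule, no imputation and no model that accepts incomplete visit records. Nor does it say that only men with all four visits are analysed. It leaves open whether the MANOVA is laid out with one row per man or one row per visit, and whether the outcomes enter jointly or one at a time.

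**The concern.** The plan expects men to be missing at the last visit and chooses methods that do not handle a missing visit well. In the usual repeated-measures layout, each man is one row and the four visits are four columns; a blank in any column removes the row. A man who completed the 8-week diet and missed only the 6-month visit would then leave the group × time analysis altogether, although his week 4 and week 8 results are on file.

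Two things are at stake. First, the men left in that analysis are selected by something that happens after randomisation. The arms eat different diets, so the number of men who leave, or their reasons, could differ by arm. Second, a by-visit t test and the MANOVA could disagree at week 8 simply because they use different men, and the plan does not say which would then be believed.

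**Working it through.** **Inputs from the documents.** 38 men per arm, 10% loss by 6 months, four visits, power 80%, α 0.05.

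**The plan's own sample size.** The 35 per group cannot be rebuilt, because a 40% improvement with SD 2 gives no absolute difference. By the exact two-sided t test (sidedness assumed), 35 per group at 80% power corresponds to 0.68 SD. The dropout step gives 35/0.9 = 38.9, so 39; the text adds 2 to 35, which is 37, yet states 38. That is a separate matter and nothing below depends on it.

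**Data discarded by a complete-case run.** Expected loss is 76 × 0.10 = 7.6 men, about 4 per arm, which leaves about 34. If all leave after week 8, the run discards 7.6 × 2 = 15.2 observed post-baseline values per outcome, plus about 8 baseline values.

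**Precision.** The standard error rises by 1/√0.9 = 1.054, about 5%. At 0.68 SD, power is 83.2% with 38 per group, 80.0% with 35 and 78.8% with 34. This loss is small.

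**Size of a possible bias (assumed scenario).** No diet effect, correlation 0.7 between visits, 4 lost per arm after week 8, random loss in one arm.

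- Strong selection: the other arm loses its lowest 10% at week 8. The mean of those kept shifts by φ(1.2816)/0.9 = 0.195 SD at week 8, and by 0.7 × 0.195 = 0.14 SD at 6 months.
- Milder selection: loss depends on the week 8 value plus equal noise. The correlation with the week 8 value is 1/√2 = 0.707, so the shift is 0.195 × 0.707 = 0.14 SD.

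Simulated results (8,000 trials per run; Monte Carlo error about 0.3 percentage points):

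| Quantity | Strong selection | Milder selection | Random loss |
|---|---|---|---|
| Completer-only week 8 bias | about 0.19 to 0.20 SD | about 0.14 SD | 0 |
| Type I error, complete-case group main effect | 12 to 13% | about 9% | about 5% |
| Type I error, complete-case group × time | 6 to 7% | about 6% | about 5% |
| Type I error, week 8 t test on all men seen | about 5% | about 5% | about 5% |

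A repeat run for this write-up gave 8.2% (group main effect) and 5.4% (group × time) under milder selection, so the lower ends are approximate. Under strong selection, using all observed visits gave a bias of 0.005 SD at week 8, and a likelihood-based estimate gave 0.003 SD at 6 months.

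**Other loss patterns.** Assume a true difference of 1.36 with SD 2, and loss related to the week 8 value plus equal noise. The completer-only week 8 bias is:

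- 10%/10%, same mechanism: 0.00
- 5%/15%: -0.24 (-17%)
- 0%/20%: -0.49 (-36%)
- 10%/10%, opposite mechanisms: -0.55 (-40%)

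Bias therefore needs a difference between arms in rate or mechanism.

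**The other layout.** With time and group as factors and one row per visit, a missed 6-month visit removes one row and the earlier values stay. But a man's four visits are then treated as independent, which is wrong for repeated measurements on the same man.

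**The case against.** The strongest reply is that complete-case analysis is not in the plan's text. It is inferred from the usual layout and the software default, and the MANOVA sentence can be read as long format. This stands, and so the point is worded as a default. It does not rescue the plan, because the long-format reading has its own fault.

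A reader might infer that week 4 and week 8 data are lost from every diet comparison. The documents do not support that. Inter-group effects are assigned to Student's t test, which, if run by visit, keeps every man seen at that visit. A reader might also take rANOVA as a biased diet comparison, but "repeated measures (rANOVA) was used to calculate the intra-group effects": it compares visits within an arm and does not itself compare diets.

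A reader might infer that the plan's diet test has a false-positive rate near 15%. That figure belongs to a week 8 t test restricted to 6-month completers, which the plan does not name. Under the same strong selection, the complete-case group × time test is only slightly inflated; the group main effect is affected more.

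Finally, nothing in the documents shows that loss differs between arms, and the scenarios are assumptions. That stands too. Different diets make such a difference plausible, not established.

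**Conclusion.** The concern holds in limited form. The plan expects 10% loss and states no missing-data handling. In one common layout its MANOVA discards observed week 4 and week 8 values; in the other it ignores within-man correlation. The within-group rANOVA, run one row per man, discards the same values. By-visit t tests would not, so the analyses can rest on different sets of men.

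Bias in the MANOVA group comparison is possible, not shown. With outcome-related loss in one arm only, it is about 0.14 to 0.20 SD at week 8; the upper end is about 29% of the 0.68 SD design effect (0.195/0.68). Type I error is then about 9 to 13% for the group main effect and 6 to 7% for group × time. Under random loss there is no bias and the error is about 5%. These figures rest on the assumed correlation of 0.7, 4 men lost per arm after week 8, and the assumed selection rules. The case for change rests on possible bias and inconsistent analysis sets, not on lost power.

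**What to change.** Replace the 4 × 2 MANOVA and the rANOVA with a linear mixed model for repeated measures (SPSS MIXED), fitted to each outcome separately. Use group, visit and group × visit as fixed effects, with an unstructured covariance across visits. Include every randomised man in his assigned group with all visits observed. Take the between-diet difference and the within-group change at each visit from this model, so that all results rest on one set of men.

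The cost is new analysis wording and a different procedure in the same software, with no new data and no more men. The small downside is that the model assumes data are missing at random given the observed visits.

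The Design section says the study ran to November 2021 and the document is dated 12/02/2022. The change should therefore be declared as made after data collection, with the MANOVA kept as a supporting result if it has already been run.

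### The trial is sized on handgrip alone, but the first between-diet test listed is a MANOVA of primary and secondary variables, and no handgrip comparison is given precedence over it

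*Combined protocol and SAP*

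**What the plan says.** **Sizing.** The Sample size section uses one variable: "Thirty-five subjects in each group were found by assuming forty percentage mean improvement in handgrip strength with standard deviation of 2". It adds: "The sample size was calculated with the statistical power at 80% with α level of 0.05". The number randomised is 76, or 38 per group.

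**Outcomes.** The Outcome measures section lists handgrip, muscle cross-sectional area at three sites (biceps, quadriceps, calf), TSK-11 and SarQoL. That is four outcome types, or six variables if each muscle counts separately. None is labelled primary. On TSK-11, "Maximum score indicates high level of fear whereas the minimum score indicates low level of fear during activities", so a rise is unfavourable there and favourable for grip.

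**Analysis.** The Statistical analysis plan has four measurement times: baseline, 4 weeks, 8 weeks and 6 months. It first names a 4 × 2 time-and-group "multiple analysis of variance (MANOVA) of primary and secondary variables are reported between group A and group B at various intervals". The next sentence says "Student's t test was used to calculate inter-group effects" and gives repeated-measures ANOVA for change within groups. Means, SDs and 95% CIs are to be shown. The software "was used to do all the statistical tests and α level was set at 0.05". The plan does not say which test, outcome or visit decides between the diets.

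**The concern.** The power calculation and the first-listed between-diet test appear to address different questions. The first concerns handgrip. The second, read as a joint test, has as its null hypothesis that the diets differ on none of the outcomes. Rejecting that null does not identify grip as the source, and failing to reject it does not settle grip. The statistic also carries no sign, and the outcomes do not share a favourable direction.

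What is at stake is the basis of the diet conclusion. There are two between-diet procedures at 0.05, with no order between them and neither tied to the sized comparison. If they disagree, the plan gives no rule, and a claim for one diet could rest on a secondary scale.

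**Working it through.** **1. Can the 35 per group be reproduced?** Inputs from the Sample size section: 40% improvement, SD 2, 80% power, α 0.05. No baseline mean, no difference in kg and no sidedness are stated, nor whether the 40% is a difference between diets. Two-sided, two-sample t test:

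- Difference 0.4 with SD 2 (d = 0.2): 394 per group.
- d = 0.4: 100 per group.
- 40% of the 24 kg entry limit for grip is 9.6 kg, so d = 9.6/2 = 4.8: only a few subjects.

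None of these gives 35. Working backwards, 35 per group has 80% power at d = 0.679, or 0.679 × 2 = 1.36 kg. That would be 40% of a baseline of 1.36/0.4 = 3.4 kg. I use d = 0.679 below only because it grants the plan its 80%; it is an assumption.

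The dropout step does not add up either: 35 + 2 = 37, not 38, while 35/0.9 = 38.9, or 39. The results are therefore given at both 35 and 38 per arm.

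**2. Power of a joint test with that grip effect.** A two-group MANOVA of p variables at one visit is Hotelling's T². Its power comes from a noncentral F with p and 2n − p − 1 degrees of freedom and noncentrality (n/2)·D², where D² = δ′R⁻¹δ. If only grip differs and all correlations equal r,

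D² = d²·[1 + (p − 2)r] / {(1 − r)[1 + (p − 1)r]}.

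Example: p = 6, r = 0, n = 35 gives D² = 0.679² = 0.46, noncentrality 17.5 × 0.4615 = 8.08, and power 48.9%. The documents give no correlations, so r runs from 0 to 0.5:

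| Test | n per arm | r = 0 | r = 0.3 | r = 0.5 |
|---|---|---|---|---|
| Handgrip t test | 35 | 80.0% | – | – |
| Handgrip t test | 38 | 83.2% | – | – |
| Joint, 4 variables | 35 | 57.4% | 66.6% | 80.3% |
| Joint, 4 variables | 38 | 61.7% | 71.0% | 84.1% |
| Joint, 6 variables | 35 | 48.9% | 60.1% | 76.0% |
| Joint, 6 variables | 38 | 53.2% | 64.8% | 80.4% |

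(The t test involves one variable, so r does not apply.)

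**3. When the other outcomes move too.** If all six differ by 0.679 in the same statistical direction, D² = 6d²/(1 + 5r). Power at 35 per arm is then 96.0%, 90.3% and 76.0% for r = 0.2, 0.3 and 0.5. With four uncorrelated variables and d = 0.34 on the other three, it is 84.2%.

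**4. Direction and source.** D² is unchanged when δ becomes −δ, so the test cannot say which diet is better. With four uncorrelated variables, effects of +0.5, +0.5, −0.5 and −0.5 give D² = 4 × 0.25 = 1 and power 91.7%, although neither diet is better throughout. By symmetry, an effect of 0.679 on TSK-11 alone triggers the six-variable test exactly as often as the same effect on grip alone (48.9% at r = 0).

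**5. The other reading of 4 × 2.** The label could mean one multivariate repeated-measures model per variable. Take handgrip alone, three changes from baseline, d = 0.679 at all three visits. Power at 35 per arm is 90%, 82% and 74% for correlations 0.3, 0.5 and 0.7 between the changes. Nothing is pooled across outcomes, and a shortfall need not arise.

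**The case against.** The strongest reply is that the plan already contains what is being asked for. A Student's t test between groups follows in the next sentence, with means and 95% CIs, and a t test of handgrip is both single-outcome and directional. The MANOVA is only said to be reported. Nothing makes it confirmatory or a gatekeeper, and an omnibus test followed by univariate tests is common practice. This largely stands. A reader might infer that the trial has no valid handgrip comparison, and the documents do not support that. What the reply does not supply is an outcome, a visit or precedence for the t test.

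A reader might also infer that the joint test is underpowered. That is not supported either. Power depends on effects and correlations that the documents do not give. It reaches 80% at r = 0.5 with four variables at 35 per arm or six at 38, and goes well above 80% if other outcomes respond. Having only grip differ is one end of the range.

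Extending the calculation to 18 contrasts (six variables by three changes from baseline) would look worse: 26–51% if every correlation is the same value from 0 to 0.5. But changes that share a baseline are likely to be correlated. At 0.5 between visits, the range becomes 40–68%. I do not rely on either set.

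The pooled reading is the ordinary one but not the only one. Under the per-variable reading, the arguments about secondary outcomes and mixed directions fall away. What remains is that a test with several degrees of freedom over time is not the single contrast that was sized.

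Finally, the 80% itself is not shown to hold for any between-diet test, since 35 cannot be reproduced. That is correct, and it is why the fix does not simply reassign the 80%.

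**Conclusion.** The point holds in a limited form. The sizing concerns handgrip, and the first between-diet test listed does not, on the ordinary reading. That test has no direction and can be driven by a secondary outcome, and the 80% does not describe it. The handgrip comparison that the plan does allow is given neither a visit nor precedence.

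The size is illustrative. With d = 0.68 and only grip differing, joint power at one visit is 57–80% (four variables) or 49–76% (six) at 35 per arm, and 62–84% or 53–80% at 38. This rests on a back-solved effect, a two-sided test, equal correlations of 0 to 0.5 and the pooled reading. It shows that power for this test is unstated and may be well below 80%, not that it must be.

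This should be corrected because it decides how the main conclusion is drawn. It is not fatal, because a suitable comparison can be made from the tests already listed.

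**What to change.** - Take the between-diet conclusion from one between-group comparison of handgrip at one named visit, reported as a difference with its 95% CI.
- Analyse each other outcome in its own model, labelled secondary.
- Label the MANOVA descriptive and not used for conclusions, and say whether it pools outcomes or is run per variable.
- Restate the inputs behind 35 per group (difference in kg between diets, SD, sidedness) so that they reproduce the number. Then state that the power refers to the handgrip comparison only.

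The cost is SAP wording and a re-run in the same software on the same data. The loss is a single omnibus p-value across outcomes. The Design section has the trial ending in November 2021 and the document is dated 2022, so the choice of visit should be recorded as made after the trial period and justified without reference to results.
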